**B. Statistical Considerations**

This is a prospective double-blinded randomized controlled trial comparing two pre-treatment protocols for patients undergoing intradetrusor botox injections to determine if a buffered lidocaine solution offers superior pain control. We are planning as study of a continuous response variable from independent controls and experimental subjects with one control per experimental subject. In a prior study the response within each group had a standard deviation of 2.08. If the true difference between the experimental and control groups is 1.4 which would represent a 38% difference in pain scores, then we would need to enroll 36 controls and 36 experimental subjects to reject the null hypothesis that the population means of the experimental and control groups are equal with a probability (power) of 0.8. The type 1 error probability associated with this test of this null hypothesis is 0.05.

All de-identified data will be shared with BIDMC who will help with the statistical analysis. We will analyze data with SAS 9.3 (SAS Institute, Cary, North Carolina). Descriptive statistics will be presented as medians with interquartile range (IQR), median with standard deviation or proportions, depending on data type and distribution. We estimate the risk ratio (RR) and 95% confidence interval (CI) for pre-specified risk factors. All tests will be two sided and P values <0.05 will be considered statistically significant.

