**B2. SIGNIFICANCE AND BACKGROUND FOR THE STUDY**

Lidocaine is a commonly used amide-type local anesthetic. Lidocaine exists as both a quaternary water soluble structure, and a tertiary lipid-soluble structure. Only the tertiary lipid-soluble structure can cross the lipid bilayer of a cell membrane and thereby enter a neurons axoplasm and induce the desired effect. The ionization constant of lidocaine is 7.7 which means that at a pH of 7.7, 50% of lidocaine is available in the tertiary lipid-soluble structure. At a physiologic pH between 7.35 and 7.45 only around 44% of lidocaine is in the tertiary lipid-soluble structure. However, for lidocaine to be stable in solution, it is typically formulated as a hydrochloride salt and the pH of most commercially available lidocaine solutions are at a pH of 6.09. In an acidic solution the majority of lidocaine is available in the quaternary water-soluble structure and at this pH only 2.5% of lidocaine is in the tertiary lipid-soluble structure. A Cochrane review found that increasing the pH of lidocaine prior to injection decreased pain and increased patient satisfaction perhaps because of the aforementioned pharmacokinetic principles

Lidocaine is typically used as anesthetic for intradetrusor injections of onabotulinum toxin A for the treatment of refractory overactive bladder. In 2003, a technique for intradetrusor injections of onabotulinum toxin A was first described using only local anesthesia. At that time, the procedure involved intrauterthral lidocaine. The procedure has evolved since that time and currently many physicians utilize protocols with both

utraurethral and intravesical lidocaine. At baseline intradetrusor onabotulinum toxin A injections are generally well tolerated and with reported mean VAS scores around 3.

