### B3. DESCRIPTION OF RESEARCH PROTOCOL

#### A. Study Design – Overview, Methods, Procedures

**Brief overview:** This will be a prospective double-blinded randomized controlled trial comparing two pre-treatment protocols for patients undergoing intradetrusor botox injections to determine if a buffered lidocaine solution offers superior pain control.

**Study Protocol:** After approval by the IRB, providers will approach possible participants who are having intradetrusor botox injection for overactive bladder which is the standard of care for patients with refractory overactive bladder. If the patient meets eligibility criteria, consent forms will be signed and the patient will be randomized 1:1 to receive either our standard pretreatment regimen with 50 mL 1% lidocaine + 50ml of 0.9% normal saline or our buffered bicarbonate protocol with 50 mL 1% lidocaine + 45ml of 0.9% normal saline + 5 mL 8.4% sodium bicarbonate. The primary end point of this trial is to assess the pain scores measured on a Visual Analogue Scale (VAS) immediately following the procedure. Secondary end points include patient satisfaction, willingness to undergo repeat treatment and adverse events.

All subjects will be randomized 1:1 at the first intervention visit to one of the two protocols . At the completion of the procedure, patients will be asked to complete a brief questionnaire about their experience. Patients will follow up in clinic for a post-void residual check two weeks after the procedure as is standard for

MOUNT AUBURN  
HOSPITAL

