### Outcome Measures:

The **primary** outcomes measures will include:

- Pain: The Visual Analogue Scale (VAS) consists of a straight line with the endpoints defining extreme limits such as 'no pain at all' and 'pain as bad as it could be' which was first described in 1923. The patient is asked to mark his pain level on the line between the two endpoints. The distance between 'no pain at all' and the mark then defines the subject's pain. Studies vary on the definition of a clinically meaningful change in pain, but suggest that a difference of anywhere from 12% to 38% may be clinically significant

The **secondary** outcomes measures will include

- Satisfaction
- Willingness to undergo repeat procedure
- Adverse events
  - Adverse events will be collected from the medical record and include postoperative urinary tract infections, hematuria, readmission, urinary retention, number of patient phone calls
- Pelvic Floor Distress Inventory (PFDI-20) Scores
  - The short-form version of the Pelvic Floor Distress Inventory has a total of 20 questions and 3 scales (Urinary Distress Inventory, Pelvic Organ Prolapse Distress Inventory, and Colorectal-Anal Distress Inventory). Total PFDI score measured on a 0-300 scale with higher scores equal to greater pelvic floor distress. As with the Total PFDI Score, higher subscale scores equal greater pelvic floor distress, on a 0-100 scale

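### Does the plan leave its primary VAS comparison open by naming no test, effect estimate or confidence interval?

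*Combined protocol and SAP*

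**What the plan says.** The endpoint is clear. B3, section A, states: "The primary end point of this trial is to assess the pain scores measured on a Visual Analogue Scale (VAS) immediately following the procedure". Under Outcome Measures the scale is a line with a fixed lower end: "The distance between 'no pain at all' and the mark then defines the subject's pain".

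The sizing text stands under Sample size and again in B3, section B (Statistical Considerations). It describes a continuous response in independent groups with 1:1 allocation. Its inputs are "In a prior study the response within each group had a standard deviation of 2.08" and "If the true difference between the experimental and control groups is 1.4 which would represent a 38% difference in pain scores". The aim of the 36 per arm is "to reject the null hypothesis that the population means of the experimental and control groups are equal with a probability (power) of 0.8", with type 1 error 0.05.

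The analysis paragraph in section B then names the software and adds three things:

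- a sentence on summaries: "Descriptive statistics will be presented as medians with interquartile range (IQR), median with standard deviation or proportions, depending on data type and distribution";
- one effect measure: "We estimate the risk ratio (RR) and 95% confidence interval (CI) for pre-specified risk factors";
- a rule that all tests are two-sided at 0.05.

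No test, treatment-effect estimate or interval is tied by name to VAS.

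**The concern.** The sizing is on means, yet the list of summaries contains no mean, and it lets the summary depend on the distribution. The only confidence interval mentioned is for a risk ratio, which does not suit a continuous score without a cut-off.

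The distribution clause also looks live for this endpoint. If the 38% is relative to control, the plan's figures put both means within two SDs of the bottom of the scale, so skew is plausible. One analyst might report means with a t-test, another medians with a Mann-Whitney test. The two describe different effects and can fall on opposite sides of 0.05. If the choice were made by looking at the p-values, the type 1 error of the one primary comparison would rise above its nominal level.

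**Working it through.** **Inputs.** From Statistical Considerations: difference 1.4, stated as 38%; SD 2.08; 36 per arm; two-sided 0.05; power 0.8. From B2: "reported mean VAS scores around 3". Assumptions: 38% is relative to the control mean; the scale runs 0-10 (no length is given); the distribution shapes below.

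**1. Which test does the stated size belong to?**

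- Normal approximation: n = 2 × (1.960 + 0.842)² × (2.08/1.4)² = 2 × 7.85 × 2.207 = 34.65, so 35 per arm.
- Two-sample t-test (noncentral t), two-sided: 35.64, so 36 per arm. Power is 80.4% at 36 and 79.3% at 35.
- One-sided normal approximation: 28 per arm, which does not match.

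The stated 36 is the two-sided two-sample t-test on means. A Mann-Whitney test under normality would need 35.64/(3/π) = 37.3, so 38.

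**2. Is skew plausible?**

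- Control mean: 1.4/0.38 = 3.68. Treated mean: 3.68 − 1.4 = 2.28.
- Normal share below 0: Φ(−3.68/2.08) = 3.8% in control; Φ(−2.28/2.08) = 13.6% in treated.
- With a control mean of 3: Φ(−3/2.08) = 7.5%; treated mean 1.6: Φ(−1.6/2.08) = 22.1%.

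Skew is plausible, mild in control (a beta shape on 0-10 has skewness 0.40) and clearer in treated (1.03). It is not forced: the treated figure needs the SD to stay at 2.08 while the mean falls.

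**3. What does the choice of test do?** Simulated trials, 36 per arm: 100,000 per row, 10,000 for the uncapped gamma.

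| Shape | t-test power | Mann-Whitney power | Disagree at 0.05 |
|---|---|---|---|
| Normal, SD 2.08 | 80.5% | 78.2% | 5.2% |
| Beta, SD 2.08 | 79.6% | 86.2% | 7.3% |
| Gamma, SD 2.08, uncapped | 79.6% | 92.7% | 13.4% |
| Gamma capped at 10 (SD about 2.0) | 82.2% | 92.7% | 10.8% |
| Beta, treated scores × 0.62 | 93.0% | 84.3% | 8.6% |
| Capped gamma, treated scores × 0.62 | 94.9% | 91.1% | 4.4% |

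In the × 0.62 rows the treated SD falls too. Disagreement runs from about 4% to 13%.

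With means of 3.0 and 1.6 and the SD held at 2.08, it is about 15% to 18%. There 1.4/3 = 47%, not the plan's 38%, so that case departs from the plan's own effect.

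**4. Type 1 error.** In null trials:

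- t-test fixed in advance: 4.9% to 5.1%;
- Mann-Whitney fixed in advance: 4.8% to 5.0%;
- test chosen by a normality pre-test: 4.6% to 5.4%;
- smaller p-value taken: 5.7% to 6.6%.

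**5. Interval for the implied estimate.** Expected half-width = 1.994 × 2.08 × √(2/36) = 0.98 points.

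**The case for a change.** The strongest reply is that an implied test is not a stated analysis. A sample-size paragraph says how the trial was sized, and the analysis paragraph is where one looks for the test. There it is absent, along with the estimate and its interval. Reading the odd pairing of a median with a standard deviation as a slip restores the mean to the summaries but still names no test. The two routes also report different quantities: where the mean difference is about 1.4, the average difference in sample medians ran from 1.26 to 1.77. Only the mean difference can be set against the planned 1.4. Writing it down would take a few sentences.

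The omission stands as a fact. The two readings, however, do not have equal support:

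- The plan states its null hypothesis as equality of population means and attaches the 0.05 level to the test of that hypothesis. A Mann-Whitney test does not in general test equal means, so choosing it for the primary comparison would depart from the plan.
- The distribution clause opens with descriptive statistics and is tied to summaries. Nothing extends it to the test.
- The risk ratio concerns risk factors, which fits the secondary objective on predictors of high pain in B1. It is not a rival primary analysis.

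The inflation to 5.7%-6.6% needs selection by p-value, which the plan nowhere proposes.

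**Conclusion.** No change is needed. This is a gap in detail that an analyst following the plan fills sensibly, with a probable clerical slip beside it. The stated null hypothesis, two-sided 0.05 level and 36 per arm together identify a two-sample t-test. Reporting the mean difference with its 95% interval, half-width about 0.98, is the ordinary companion to that test.

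Followed this way the result is sound. Type 1 error stays near 5%, power is 80.4% under the plan's assumptions and about 79% or more in every shape tried, and the sample size is unaffected. Preferring a rank test would be a trade-off rather than a gain: it does better if pain is skewed with equal spread in both arms, and worse if scores fall in proportion.

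The sizing result rests only on the plan's figures. The power, disagreement and error figures also rest on the assumed shapes, the 0-10 scale and the 38% being relative to control. The conclusion would weaken only if the test were chosen after comparing p-values.

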**Secondary Objectives:**

1. Patient satisfaction measured on a five point Likert scale
2. Willingness to undergo procedure again measured on a five point Likert scale
3. Adverse events
4. Demographic and clinical factors that predict high pain scores during the procedure

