### Sample size:

We are planning a study of a continuous response variable from independent controls and experimental subjects with one control per experimental subject. In a prior study looking at pain associated with intradetrusor botox, the response within each group had a standard deviation of 2.08. If the true difference between the experimental and control groups is 1.4 which would represent a 38% difference in pain scores, then we would need to enroll 36 controls and 36 experimental subjects to reject the null hypothesis that the population means of the experimental and control groups are equal with a probability (power) of 0.8. The type 1 error probability associated with this test of this null hypothesis is 0.05.

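### The risk ratio names no outcome; if it serves the predictors-of-high-pain objective, it cuts the continuous VAS at an undefined threshold and loses power

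*Combined protocol and SAP*

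**What the plan says.** The last item under Secondary Objectives is: "Demographic and clinical factors that predict high pain scores during the procedure". No VAS value is given for what counts as high.

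Outcome Measures scores pain as a length on a line: "The distance between 'no pain at all' and the mark then defines the subject's pain". Statistical Considerations treats the response as continuous for sizing: "We are planning as study of a continuous response variable from independent controls and experimental subjects with one control per experimental subject".

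The only effect measure in Statistical Considerations comes in one sentence: "We estimate the risk ratio (RR) and 95% confidence interval (CI) for pre-specified risk factors". It does not say which outcome the risk ratio describes, and the section does not say which factors are meant. The Data collection section lists baseline variables (among them age, BMI, fibromyalgia, chronic pain medication, chronic back pain, myofascial pain and PFDI-20) but does not designate any of them as risk factors. The testing rule is general: "All tests will be two sided and P values <0.05 will be considered statistically significant".

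**The concern.** A risk ratio needs a yes/no outcome. Of the stated objectives, only the fourth secondary one concerns predictors, so the natural reading is that the risk ratio belongs to it and that the outcome is high pain. On that reading three things follow.

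- **Information is discarded.** A patient just above the cut and one far above it count the same.
- **Few patients may count as high.** The background section says "intradetrusor onabotulinum toxin A injections are generally well tolerated and with reported mean VAS scores around 3", so a cut in the upper half of the scale leaves a small group and wide intervals.
- **The result depends on a number nobody has fixed.** With no threshold in the plan, a reader of the results could not tell a planned cut from one chosen afterwards.

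At stake is how well 72 patients can answer one secondary question. The treatment comparison is not involved.

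**Working it through.** **Inputs from the documents.** SD 2.08 ("In a prior study the response within each group had a standard deviation of 2.08"); 36 per arm, 72 in all; two-sided 0.05; treatment difference 1.4. Control mean: about 3 from the background section, or 3.68 from the sample-size statement ("If the true difference between the experimental and control groups is 1.4 which would represent a 38% difference in pain scores"; 1.4/0.38 = 3.68).

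**Assumptions, not in the documents.** VAS scored 0-10 and roughly normal; one binary factor; its prevalence, its strength and the cut.

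**Step 1: the plan's own figure.** n per group = 2(1.96 + 0.842)² × 2.08² / 1.4² = 34.6, so 35 by the normal approximation. The noncentral t gives 36 (power 0.804; 35 gives 0.793). The stated 36 reproduces.

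**Step 2: closed-form illustration.** Take a factor present in half the patients (36 v 36) that shifts mean pain by 1.4, with reference mean 3.0. Its correlation with pain is 0.7/√(2.08² + 0.7²) = 0.7/2.19 = 0.32. Analysed as a continuous score, power is 0.80 and the 95% CI half-width is 1.96 × 2.08 × √(2/36) = 0.96 points.

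For a cut at c:

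- p0 = 1 − Φ((c − 3.0)/2.08) and p1 = 1 − Φ((c − 4.4)/2.08).
- Power = Φ{[(p1 − p0) − 1.96√(2p̄(1 − p̄)/36)] / √[(p0(1 − p0) + p1(1 − p1))/36]}, where p̄ is the mean of p0 and p1.
- The risk-ratio interval is exp{ln(p1/p0) ± 1.96√[(1 − p0)/(36p0) + (1 − p1)/(36p1)]}.

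| Cut | p0 | p1 | High-pain patients | Power | Risk ratio (95% CI) |
|---|---|---|---|---|---|
| ≥4 | 0.315 | 0.576 | 32 | 0.61 | 1.83 (1.05-3.19) |
| ≥5 | 0.168 | 0.386 | 20 | 0.55 | 2.30 (1.00-5.30) |
| ≥6 | 0.075 | 0.221 | 11 | 0.42 | 2.96 (0.80-10.9) |
| ≥7 | 0.027 | 0.106 | 5 | 0.26 | 3.88 (0.44-34.0) |

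With reference mean 3.68, power at the same cuts is 0.61, 0.60, 0.51 and 0.37. Simulating with scores clipped to 0-10 (reference mean 3.0) gives 0.81 for the t test and 0.61, 0.56, 0.44 and 0.27 for the cuts, so the bounded scale hardly matters here.

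**Step 3: wider range, both analyses adjusted for arm.** 10,000 simulated trials per scenario; prevalence p = 10-50%; control mean 3 or 3.68; treated mean 1.4 lower; scores clipped to 0-10. For correlation r the factor effect is r × 2.08/√(p(1 − p)) and the residual SD is 2.08√(1 − r²). The continuous score was analysed by linear regression on arm and factor, the cut score by a Mantel-Haenszel test stratified by arm, with cuts from >2 to >6.

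| Correlation | Linear power (%) | Points lost, best cut | Points lost, cut >5 |
|---|---|---|---|
| 0.1 | 13-14 | 1-4 | 2-6 |
| 0.2 | 37-41 | 10-13 | 10-22 |
| 0.3 | 71-74 | 15-21 | 16-42 |
| 0.4 | 92-95 | 11-15 | 11-47 |
| 0.5 | 98-100 | 4 | 4-31 |

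The continuous analysis had the higher power in every scenario. About 8 (mean 3) to 13 (mean 3.68) of the 72 patients exceed 5.

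**Step 4: analytic check.** The efficiency of a cut relative to the continuous score is φ(z)²/(q(1 − q)), where q is the proportion above the cut and z the matching normal quantile. It is 64% at the median, 49% when 20% are high and 34% when 10% are high. Even a median cut therefore carries the information of about 0.64 × 72 = 46 patients.

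**Step 5: choosing the cut afterwards.** For an unrelated factor (20,000 trials per scenario), P<0.05 occurs at one or more of >3, >4, >5 and >6 in 13-15% of trials. Any single cut gives about 3-6%.

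**The case against.** **The plan never says the VAS will be dichotomised.** This stands. Statistical Considerations also names no test for the primary VAS comparison, so its silence about regression may be brevity and not a choice. A reader might infer that the trial has decided to dichotomise pain, or that the treatment comparison will be run that way; the text supports neither. What the documents show is an unnamed outcome and an undefined threshold. The power loss is conditional on the natural reading.

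**The risk ratio may be meant for adverse events.** Urinary tract infection, hematuria, readmission and retention are naturally binary, and the risk ratio is the only effect measure in the section that suits them. This stands too, and it rules out simply deleting the sentence.

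**The objective asks about high pain, and a risk ratio answers that directly.** Partly right. A slope or mean difference describes the level of pain, which is a related but different question. That is a reason to allow a high-pain risk ratio alongside, with its cut fixed. It does not make it the only analysis.

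**The size is assumed, and the consequence is small.** Right on both counts. VAS length, predictor strength, prevalence and cut are all assumptions, and only a single binary factor was simulated although several listed variables are numeric. The direction was the same in every scenario; the amount is not fixed by the documents. Nor do they show any intention to choose a cut after seeing the data; the 13-15% describes what an open threshold permits. The objective is listed last and does not appear among the secondary end points in the study overview or under Outcome Measures.

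**Conclusion.** The point holds conditionally. The risk-ratio sentence names no outcome. If it serves the fourth secondary objective, it forces a cut of the continuous VAS at a value the plan does not state. Under the assumptions in the working, that costs roughly 10-20 points of power at the best cut for correlations of 0.2 to 0.4, and usually more at higher cuts. At very weak or very strong correlations the best-cut loss is only a few points.

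A reader might go further and conclude that the risk ratio is wrong and should be removed. The documents do not support that, since it may be the intended measure for the binary adverse events. This is a cheap improvement to a secondary analysis, of low severity.

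**What to change.** Add to Statistical Considerations, without removing the risk-ratio sentence:

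> For secondary objective 4, predictors of pain will be assessed by linear regression of the continuous VAS score on each factor designated from the Data collection baseline list, adjusted for randomised arm, reporting mean difference or slope with 95% CI; this analysis is exploratory.

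Then:

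- Mark which variables in the Data collection list are the designated factors.
- Keep the risk ratio for binary outcomes such as adverse events, and name those outcomes in the sentence.
- If a high-pain risk ratio is also reported, state its VAS cut-off before unblinding and label it supportive.

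The cost is wording only, with no new data, visits or patients. The downside is that a mean difference or slope speaks to how much pain patients report, and only indirectly to whether it is high.

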**Data collection:**

Baseline characteristics collected from the medical records and collected as part of routine clinical care for every patient:

- Age (years),
- Gravid (numeric value),
- Para (numeric value),
- BMI (height and weight)
- Race/ethnicity
- Medical history (fibromyalgia, use of chronic pain medications, chronic back pain)
- Surgical history (hysterectomy, prolapse surgery, urinary incontinence surgery)
- Pre-treatment Kegel strength
- Pre-treatment myofascial pain
- Pre-treatment POPQ
- Pre-treatment PFDI-20

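### One unadjusted P<0.05 rule covers every test, so secondary and risk-factor results would be declared significant on the same footing as the primary VAS comparison

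*Combined protocol and SAP*

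**What the plan says.** Section B3, B. Statistical Considerations, ends with the rule "All tests will be two sided and P values <0.05 will be considered statistically significant". The same section ties the planned error rate to a single comparison: "The type 1 error probability associated with this test of this null hypothesis is 0.05". That comparison is mean VAS pain between arms, with 36 patients in each.

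The other analyses are spread over three places:

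- Secondary Objectives (B1) lists satisfaction, willingness to repeat, adverse events, and "Demographic and clinical factors that predict high pain scores during the procedure".
- Outcome Measures (B3.A) breaks adverse events into five items (urinary tract infection, hematuria, readmission, urinary retention, number of phone calls) and adds PFDI-20.
- Statistical Considerations promises, for the predictor objective, "We estimate the risk ratio (RR) and 95% confidence interval (CI) for pre-specified risk factors".

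The factors are not named there. The only candidate list is under Data collection, introduced as "Baseline characteristics collected from the medical records and collected as part of routine clinical care for every patient". It does not say that each item will be tested. No cut-off for a high pain score is given, although a risk ratio needs one.

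**The concern.** The rule says all tests. Nothing in the text adjusts for multiplicity, orders the tests or calls any analysis exploratory. Followed literally, a secondary difference or a predictor that reaches P<0.05 by chance is declared statistically significant in the same terms as the primary result.

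The trial has 72 patients and was sized for one comparison. Predictors of high pain are a stated objective, so claims about them are foreseeable. Because neither the factor list nor the high-pain cut-off is written down, the number of tests is open. At stake is the standing of the secondary and predictor findings, not the primary conclusion.

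**Working it through.** **Step 1. Reproduce the plan's own figure.** Inputs from Statistical Considerations: difference 1.4, SD 2.08, power 0.80, type 1 error 0.05, equal arms.

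- Normal approximation: n = 2 × [2.08 × (1.960 + 0.842) / 1.4]² = 34.65, so 35 per arm.
- Two-sample t-test: 35.64, so 36 per arm, with power 0.804 at 36.
- A one-sided test would need only 28 per arm.

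The stated 36 per arm is therefore one two-sided t-test at 0.05. The sample size allows for no other test.

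**Step 2. Count the possible tests.** The plan gives no number, so this count is inferred.

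- Outcomes: 2 Likert items + 5 adverse-event items = 7.
- Baseline items under Data collection: age, gravid, para, BMI, race/ethnicity (5); fibromyalgia, chronic pain medication, chronic back pain (3); hysterectomy, prolapse surgery, incontinence surgery (3); Kegel strength, myofascial pain, POPQ, PFDI-20 (4). Total 15, if each is one test.
- PFDI-20 is counted once, as a baseline item. Outcome Measures lists it as a secondary outcome, but Data collection schedules it only before treatment and no later collection is described in the text available.

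**Step 3. Chance of at least one false positive** if all k nulls are true and the tests are independent: 1 − 0.95^k.

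| Set tested | k | Chance |
|---|---|---|
| 7 outcomes only | 7 | 0.30 |
| 7 outcomes + 5 factors | 12 | 0.46 |
| 15 baseline items only | 15 | 0.54 |
| 7 outcomes + 15 baseline items | 22 | 0.68 |

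For k = 22 the expected number of false positives is 22 × 0.05 = 1.1. The chance first passes one half at k = 14 (0.512; k = 13 gives 0.487).

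**Step 4. Relax the assumptions for the 22-test case.** The correlations and event rate below are assumed, because the documents give none.

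- *Correlated tests* (simulated normal statistics; 0.3 to 0.7 among outcomes, 0.1 to 0.3 among factors, gravid with para 0.8): 0.55 to 0.65.
- *Rare adverse events.* With 36 per arm and a 5% event rate, Fisher's exact test has a true size of about 0.003, so the four yes/no adverse events add almost nothing. That leaves 18 tests: 1 − 0.95^18 = 0.60 if independent, and 0.52 to 0.58 with correlations of 0.3 to 0.5 among outcomes and 0.1 to 0.3 among factors.
- *Strong common correlation* across all 22 statistics: 0.51 at 0.4 and 0.44 at 0.5.

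Moderate correlation, with or without rare adverse events, therefore gives 0.52 to 0.65, or roughly 0.5 to 0.7.

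**The case against.** The strongest reply is that the plan does label one primary endpoint, lists the others as secondary, and ties the 0.05 error to the primary test alone. That test is not inflated, and this part stands in full. Risk factors are also already to be reported with confidence intervals, which is part of the remedy. The interval does not remove the problem, however, because the significance rule still applies to any test of those factors.

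A reader might go further and infer that the plan contains 22 to 26 tests and that a false significant finding is more likely than not. The documents do not support that:

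- No number of tests is stated, and the baseline list is a data-collection list. The upper figure also needs four PFDI-20 outcome tests, which a score scheduled only before treatment cannot supply.
- Passing one half needs about 14 or more independent tests with true nulls, or more if they are correlated. Some nulls may be false: fibromyalgia, chronic pain medication and myofascial pain are plausible predictors of pain.
- Section B5 expects the procedural risks not to differ between protocols, so the adverse-event items read as safety description more than as efficacy claims.

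A reader might also infer that any single positive secondary result is probably spurious. That does not follow. The chance of at least one error in a family of tests is not the chance that a given positive is false, which depends on prior plausibility and power.

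**Conclusion.** The concern holds in limited form. The plan applies one unadjusted significance rule to every test and does not mark the secondary outcomes or the predictor analysis as exploratory.

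The size depends on how many tests are run. With true nulls and independence it is about 0.30 for the seven outcomes alone (less if adverse events are rare), 0.46 with five factors added, and 0.68 with all 15 baseline items added. The last figure becomes roughly 0.5 to 0.7 under moderate correlation and rare adverse events, and falls below one half under a strong common correlation. All of these exceed the 0.05 that the plan sets for its single sized test.

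The primary VAS comparison keeps its 0.05 error and the trial's main conclusion is unaffected. The point deserves correction because it is easy to settle in advance and hard to repair once results are known.

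**What to change.** Replace the closing sentence of Statistical Considerations with:

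> The primary VAS comparison is tested two-sided at 0.05 and is the only confirmatory test. Secondary outcomes and risk factors are exploratory, reported as estimates with 95% confidence intervals that are not adjusted for multiplicity, and will not be used to claim a statistically significant effect or predictor.

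Then, before unblinding:

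- Name the risk factors and define the high-pain cut-off used for the risk ratios.
- If a formal predictor claim is wanted, apply Holm across that named list. The smallest P value would need to fall below 0.05/5 = 0.01 for five factors, or 0.05/15 = 0.0033 for fifteen.
- State whether PFDI-20 is a baseline covariate only or will also be collected after treatment.

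The cost is a few sentences. No patients, data or primary power are lost. The small downside is that secondary and predictor results cannot be presented as confirmed findings.
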